#### 9.2.2 Exclusion Criteria

To be eligible, the patient must not meet any of the following criteria:

##### General

1. Females that are
  - a. pregnant, or are breast-feeding (for EU countries only);
  - b. of childbearing potential, pregnant, or are breast-feeding (for US and Rest of World countries).  
*Females of childbearing potential using adequate birth control, as determined by their Health Care Provider, will be eligible.*
2. A disability that may prevent the patient from completing all study requirements.
3. Current participation in another clinical study with another investigational drug.

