Inclusion and Exclusion Criteria	
Inclusion Criteria
 
 
1. Patient completed the double-blind period in the IEDAT-02-2015 trial and must have completed the final (Visit 15/Month 12) efficacy assessments of IEDAT-02-2015 or discontinued the study during the COVID-19 pandemic.
 
2. Patient tolerated the study medication, without any evidence of steroid adverse events, or treatment-related severe/ serious adverse events.
 
3. Body weight > 15 kg.
 
4. The patient and his/her parent/caregiver (if below the age of consent), or a legal representative, has provided written informed consent to participate. If consent is provided solely by the caregiver in accordance with local regulations, the patient must provide assent to participate in the study.
 
5. Patient does not present safety contraindication for continuation of treatment, as determined by the Principal Investigator (PI) according to the procedures described below.
 
 
Procedure for selecting patients for further treatment in IEDAT-03-2018
 
 
• The Principal Investigator will ask all patients who meet the above requirements, and determine their interest in continuing to receive treatment with the study medication in a new protocol. The Principal Investigator will then determine the eligibility of the patients on the basis of his/her clinical judgement of patients' status and their safety.
 
 
Exclusion Criteria
 
General
 
 
1. Females that are       
 
a. pregnant, or are breast-feeding (for EU countries only);
 
b. of childbearing potential, pregnant, or are breast-feeding (for US and Rest of World countries).
 
 
Females of childbearing potential using adequate birth control, as determined by their Health Care Provider, will be eligible.
 
 
2. A disability that may prevent the patient from completing all study requirements.
 
3. Current participation in a clinical study with another investigational drug.
 
 
Medical History and Current Status
 
 
4. CD4+ lymphocytes count <400/mm^3 (for patients 6 years of age) or <150/mm^3 (for patients > 6 years). In presence of oral infections, like oral candidiasis, documented at the screening or recurrent as per medical history documentation, the limit increases to <200/mm^3 (for patients > 6 years).
 
5. Current neoplastic disease.
 
6. Severe impairment of the immunological system.
 
7. Severe or unstable pulmonary disease.
 
8. Uncontrolled diabetes.       
Patients with diabetes that has been stabilized (i.e. no hypoglycemic or hyperglycemic episodes in the past 3 months) will be eligible.
 
 
9. Any other severe, unstable, or serious disease or condition that in the Investigator's opinion would put the patient at risk for imminent life-threatening morbidity, need for hospitalization, or mortality.
 
10. Eligibility of patients with abnormal laboratory test values will be determined by the Investigator.
 
11. Confirmed hemoglobinopathies, e.g. hemoglobin C disease, sickle cell
 

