The onset of symptoms becomes evident in early childhood when children demonstrate unsteadiness while walking, or swaying when standing still or sitting. Most children with AT have stable neurologic symptoms for the first 4 to 5 years of life, but begin to show increasing problems in early school years. Oculomotor apraxia, slurred speech, and difficulties in swallowing appear in late pre-school and early school age children. AT patients are unable to control their muscles by the time they are 10 to 12 years of age, and this may lead to problems with fine motor functions (writing, coloring, and using utensils to eat), and slurring of speech (dysarthria) that usually stop progressing after the age of about 12 to 15 years. Most AT patients are restricted to wheelchair use for ambulation around this age. Involuntary movements such as tremors, myoclonic jerks, dystonia, chorea, athetosis, etc., are variable in the age of onset and rate of progression. (Boder, 1985; Perlman et al, 2003; Chun and Gatti, 2004) The immune system becomes progressively weaker, and recurrent respiratory infections and blood cancers are noted in late-stage patients. There is high variability in life-expectancy; however, most patients die around the age of 25 years, largely due to chronic lung disease or malignancies. (Poupard, 2003; Crawford et al, 2006)

The exclusion criteria for the study are designed to exclude patients who would be at increased risk for an adverse outcome related to treatment with EDS-EP or their participation in the trial due to their medical history/current status or use of concomitant medication. Dexamethasone has teratogenic potential in rodents; therefore, females of childbearing potential will be included only if they are practicing adequate contraception, as described at [Section 9.2.2](#). Pregnant women will be excluded. Dexamethasone is excreted in breast milk; therefore, patients who are breast-feeding are also excluded. Patients with AT are at increased risk of neoplastic and immunological diseases due to the decreased ability of the ATM gene to repair DNA; therefore, patients with these conditions are excluded.

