**14.4 Pregnancy**

This study will exclude pregnant and breast-feeding patients, and females of childbearing potential, unless they are practicing adequate contraception, as determined by their Health Care Provider. As a further precaution, a serum pregnancy test will be performed at Months 6, 12 and safety follow up visits for all young women who have had a menstrual period within the past year. Results of the pregnancy tests at IEDAT-02-2015 final visit must be negative for the patient to be randomized to treatment.

If a patient becomes pregnant during the study, she will be discontinued from the study immediately. Patients and their parents/caregivers should be instructed to notify the Investigator if it is determined that, after completion of the study they have become pregnant, either during the treatment phase of the study or within 30 days of completing the study. Whenever possible a pregnancy should be followed to term, any premature terminations reported, and the status of the mother and child should be reported to the CRO or EryDel after delivery.

Based on the estimated half-life of dexamethasone given with the EDS, i.e. less than 4 days, a period of one month of continued contraception should follow after study conclusion or early termination due to any reason.

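### At EU sites, exclusion criterion 1 lets in patients of childbearing potential who use no contraception, whom Sections 7.3 and 14.4 exclude everywhere

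*Protocol*

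**What the plan says.** Exclusion 1 has two regional limbs, worded alike in Section 9.2.2 and in the synopsis.

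- Limb 1a, for EU sites, covers females who are "pregnant, or are breast-feeding (for EU countries only").
- Limb 1b covers females who are "of childbearing potential, pregnant, or are breast-feeding (for US and Rest of World countries").
- An italic note under both limbs adds: "Females of childbearing potential using adequate birth control, as determined by their Health Care Provider, will be eligible".

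Two other sections state a contraception rule with no regional limit.

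- Section 7.3, Rationale for the Patient Population: "Dexamethasone has teratogenic potential in rodents; therefore, females of childbearing potential will be included only if they are practicing adequate contraception, as described at", followed by a cross-reference to Section 9.2.2.
- Section 14.4: "This study will exclude pregnant and breast-feeding patients, and females of childbearing potential, unless they are practicing adequate contraception". The same section says that "a period of one month of continued contraception should follow after study conclusion or early termination due to any reason".

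**The concern.** The entry criteria and the text that explains them give different answers for the same patient. Section 7.3 relies on 9.2.2 for a condition that 9.2.2 does not state at EU sites.

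Section 9.2.2 opens by making eligibility depend on meeting none of the listed exclusions. Section 16.2.1 describes the trial population by the selection criteria of Section 9.2, and Section 11.2 has each patient evaluated against the eligibility criteria at baseline. A site that works from that list, as these sections invite it to, would not meet the contraception condition in the EU limb. A site that also reads 14.4 would.

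What is at stake is fetal exposure to dexamethasone, the risk that the protocol itself names as the reason for requiring contraception. Treatment is monthly and may run past 12 months with no fixed end. The enrolment would also be hard to see afterwards: the listing in SAP Section 10.2.1 shows patients who failed an inclusion or exclusion criterion, and this patient fails none.

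**Working it through.** No arithmetic beyond a count applies. The check follows one patient through the text: a female of childbearing potential, not pregnant, not breast-feeding and not using contraception.

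**Step 1. Exclusion 1 at an EU site.** Limb 1a names only pregnancy and breast-feeding, so she does not meet it. Limb 1b does not apply in the EU. The italic note says who may enter, not who may not. The notes under exclusions 8 (stabilised diabetes) and 14 (inhaled, intranasal and topical steroids) have the same form: an exclusion is stated and an exception is then allowed. Limb 1a contains no childbearing-potential exclusion for the note to qualify.

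**Step 2. The other numbered criteria.** There are 5 inclusion criteria (9.2.1) and 16 exclusion criteria (9.2.2), so 5 + 16 = 21.

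- Criteria that expressly exclude her at an EU site: 0.
- Criteria that could reach her by discretion: 1. This is inclusion 5, under which the investigator decides whether there is a safety contraindication; it does not mention contraception.
- Exclusion 15 refers to medication prohibited by the protocol. Section 11.7 mentions birth control only among the permitted drugs.

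**Step 3. The texts side by side.**

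| Text | EU site | US or Rest of World site |
|---|---|---|
| 9.2.2 and synopsis, exclusion 1 | not excluded | excluded (1b) |
| Section 7.3 | excluded | excluded |
| Section 14.4 | excluded | excluded |

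The conflict is confined to the EU column. That column is not empty: SAP Section 8.2.1.4 lists Belgium, Germany, Italy, Poland and Spain among the participating countries.

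**Step 4. Whether another safeguard supplies the condition.**

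- For patients who finished the parent study: "Results of the pregnancy tests at IEDAT-02-2015 final visit must be negative for the patient to be randomized to treatment". Those who did not finish it have a serum test at screening (Section 11.4.1).
- Under Table 2, note d, a negative urine test is needed at baseline, a urine test precedes every infusion, and serum tests follow at Months 6 and 12 and at safety follow-up.
- Section 14.4: "If a patient becomes pregnant during the study, she will be discontinued from the study immediately".

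These measures detect a pregnancy or respond to one. They do not prevent exposure around conception between monthly infusions. Apart from the sentences in 7.3 and 14.4 that conflict with exclusion 1, nothing requires contraception during treatment.

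**The case against.** The strongest reply is that the rule is already in the protocol. Section 14.4 states it for the whole study and 7.3 repeats it. Section 9.2.2 is also not the only place where this protocol bars patients: suicidal ideation (13.7), a failed ACTH stimulation test at screening (11.4.1) and a positive baseline pregnancy test (Table 2, note d) all sit outside the list. A site that reads only 9.2.2 would miss those too. This stands, and it is why the point is a conflict between sections and not a missing rule. It does not remove the conflict, because 7.3 sends the reader to 9.2.2 for the contraception condition, and at EU sites the condition is not there.

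A second reply is that the italic note follows both limbs, has no regional limit, and would have nothing to do in the EU unless it implied that non-users are ineligible. That reading makes all three sections agree and may be what the authors meant. But it asks an EU site to infer an exclusion from a sentence worded as a permission.

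A third is that practical exposure cannot be shown. All patients come from the parent trial, whose contraception criteria are not in these documents. If that trial required contraception, few or no such patients would arrive. This also stands, and it limits the size of the problem. The regional split may be deliberate, but no reason for it is given. The sponsor's phase II study, run at two Italian centres, excluded females not using adequate contraception (Section 7.1.3.1), so a uniform rule has already been used in the EU.

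**Conclusion.** The concern holds. As written, exclusion 1 gives the wrong enrolment decision at EU sites, judged against the protocol's own rule in 7.3 and 14.4. It should be fixed.

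The number affected is unknown and probably small. The upper bound is the EU, female, childbearing-potential, non-contracepting part of an estimated maximum of 150 patients, and that group may be empty. No endpoint, analysis set or statistical result depends on it.

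Two assumptions underlie this: that sites judge eligibility mainly on the Section 9.2 criteria, and that the italic note carries its literal, permissive meaning. The textual conflict is certain. Whether it led, or would lead, to any enrolment cannot be determined from these documents.

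**What to change.** Drop the regional split in exclusion 1, in Section 9.2.2 and in the synopsis. Exclude in every region a female who is pregnant, who is breast-feeding, or who is of childbearing potential and is not on birth control that her health care provider judges adequate. Sections 7.3 and 14.4 can then stay as they are.

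If the EU difference is intended, leave exclusion 1 alone and state the difference in 7.3 and 14.4, including whether the month of contraception after the study applies at EU sites.

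The cost is one line in each of two places, or one sentence in each of two sections. Neither route needs a new visit, test or procedure.

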##### Medical History and Current Status

4. CD4+ lymphocytes count <400/mm^3 (for patients 6 years of age) or <150/mm^3 (for patients > 6 years). In presence of oral infections, like oral candidiasis, documented at the screening or recurrent as per medical history documentation, the limit increases to <200/mm^3 (for patients > 6 years).
5. Current neoplastic disease.
6. Severe impairment of the immunological system.
7. Severe or unstable pulmonary disease.
8. Uncontrolled diabetes.  
*Patients with diabetes that has been stabilized (i.e. no hypoglycemic or hyperglycemic episodes in the past 3 months) will be eligible.*
9. Any other severe, unstable, or serious disease or condition that in the Investigator's opinion would put the patient at risk for imminent life-threatening morbidity, need for hospitalization, or mortality.
10. Eligibility of patients with abnormal laboratory test values will be determined by the Investigator.
11. Confirmed hemoglobinopathies, e.g. hemoglobin C disease, sickle cell anemia, or thalassemia.
12. Moderate or severe renal and/or hepatic impairment.
13. Patients who experienced moderate/ severe steroid side effects, or moderate/ severe adverse events associated with the study medication administered in the IEDAT-02 study.

*Prior/Concomitant Medication*

14. Requires treatment with an oral or parenteral steroid. *Treatment with inhaled or intranasal steroids for asthma or allergies, as well as use of topical steroids will be permitted.*
15. Requires any other concomitant medication prohibited by the protocol.
16. Use of any drug that is a strong inducer/inhibitor of CYP3A4.

### 9.3 Premature Discontinuation

Patients who discontinue from the study prematurely must have their reason for discontinuation entered in the Case Report Forms (CRFs). Patients who discontinue from the study after having received a dose of study medication will not be replaced.

All patients who discontinue prematurely will be asked to return for the Safety follow up visit.

### 9.4 Record of Study Participants and Screening Failures

The investigator will be required to maintain a confidential record of all study participants, including all patients who were screened for the study, but were not enrolled to treatment. The confidential record must include sufficient information so that it would be possible to contact the study patient. Information on patients who have signed ICFs, but have failed screening, should be entered on the Screen Failure CRF.

The primary reason for screen failure will be recorded using the following categories:

- Did not meet entry criteria
- Major protocol deviation
- Pre-treatment Event/Adverse Event
- Lost to follow-up
- Voluntary withdrawal (specify reason)
- Study termination
- Other (specify reason).

Patients will keep the same screening number assigned during the IEDAT-02-2015 Study.

## 10 STUDY MEDICATION

### 10.1 CCI [REDACTED]

CCI [REDACTED]

[REDACTED]

### 10.1.2 CCI [REDACTED]

CCI [REDACTED]

### 10.1.3 CCI [REDACTED]

CCI [REDACTED]

CCI [REDACTED]

[REDACTED]

CCI [REDACTED]

[REDACTED]

[REDACTED]

CCI

10.2 CCI

A description of the EDS and details of the procedure for the encapsulation process are provided in [Appendix 5](#).

#### **10.6 Occupational Safety**

There are no risks anticipated related to the study medication for the staff involved in administering EDS to the patients in this study. Standard procedures and precautions for handling needles and biological samples should be followed.

## 11 EVALUATIONS AND PROCEDURES

### 11.1 Written Informed Consent

Written Informed Consent must be obtained from the patient and his/her parent/caregiver (if below the age of consent), or legal representative (if necessary), at baseline prior to initiating any study procedures required by the protocol, according to the procedure described in [Section 17](#).

This process should be performed at screening only for patients which will be enrolled without completing the ATTeST trial (i.e. who were discontinued from the Study IEDAT-02-2015 during the COVID-19 pandemic), and who may not have final evaluations for IEDAT-02-2015 study (Visit 15/Month 12); these patients will have to undergo a screening phase before the baseline visit, therefore consenting should be performed before any screening related procedure takes place.

If consent is provided solely by the caregiver in accordance with local regulations, the patient must provide assent to participate in the study. The details of the study should be discussed with the patient and parent/caregiver or legal representative (if necessary) prior to obtaining informed consent, and the Informed Consent Form (ICF) must be signed and dated by the patient, parent/caregiver/ legal representative (if necessary), and by the Investigator or his/her designee. A copy of the signed ICF will be provided to the patient, and the original will be retained with the source documents.

### 11.2 Study Conduct

The structure of this study open-label extension treatment study, as well as a detailed listing of the assessments and procedures to be performed at each visit is provided in [Section 11.4](#). The same scheme and assessments will be replicated for the second year onwards.

As a results of the COVID-19 pandemic, temporary changes to the protocol have been implemented. These changes are described in [Appendix 13](#).

#### *Screening phase*

Applicable only for patients which will be enrolled without completing the ATTeST trial.

After providing consent/assent, as described in [Section 11.1](#), patients will enter the screening phase. The screening phase will last at maximum 30 days. Any previous treatments with corticosteroid compounds will be withdrawn (washout from previous treatment), while for other patients the screening phase may coincide with the screening visit (1 day long, provided that all the required laboratory reports are available and reviewed before the eligibility confirmation at the baseline). As soon as all screening assessments/procedures have been performed and eligibility is confirmed, the patients can undergo the baseline visit.

The screening evaluation described in [Section 11.4](#) will be performed.

If any abnormal laboratory test results, vital sign measurements, or ECG findings of clinical significance are noted at the screening visit, these must be repeated during the 30-day screening period and the results made available prior to making the final decision on a patient's eligibility for the study at Baseline. Adverse events, reported by the patient or observed by the investigator, and the use of concomitant medication will be recorded from the time of signing the informed consent through the end of the study.

#### *Baseline*

Final evaluations for the IEDAT-02-2015 trial will serve as baseline evaluations for patients continuing in the IEDAT-03-2018 study. The following "baseline" assessments for IEDAT-03-2018 will be done as part of the final Vist 15 evaluation in Study IEDAT-02-2015: physical/neurological examination; 12-lead

standard ECG; laboratory evaluations [including hematology, clinical chemistry, urinalysis, serum pregnancy test (women of childbearing potential); special laboratory tests: HbA1c, CD4+ lymphocytes count and CRP]; assessment of physical development, sexual maturation, and the effect of treatment with dexamethasone on these aspects (Tanner scale); ICARS; CGI-S; CGI-S; VABS: EQ-5D-5L; C-SSRS; BMD; review of AEs and concomitant medications.

After providing consent/assent, as described in [Section 11.1](#), each patient will undergo evaluation of the eligibility criteria at the baseline visit, and if eligible, will proceed with the EDS-EP infusion. Demographic information will be rolled over from the IEDAT-02-2015 eCRF and rechecked by the Investigators for consistency, as well as medical history.

Before the EDS-EP infusion, all patients will undergo vital signs evaluation, hemolysis panel (on the diverted blood sample, see [Section 11.5](#)) and assessment of prior and concomitant medication and AEs. Women of childbearing potential must undergo a urine pregnancy test. .

CCI  
[Redacted text block]

Study treatment administration by IV infusion will be performed within 30 min after the EDS process has been completed.

CCI  
[Redacted text block]

After completion of the IV infusion of the study treatment the following assessments will be performed on Day 0 (Baseline/Visit 1): Vital signs, physical examination (1-2 hr after infusion), assessment of AEs, and assessment of concomitant medications.

*Months 1-5 and 7- 11*

Before the EDS-EP infusion, patients must undergo to laboratory tests: the diverted blood sample (see [Section 11.5](#)) will be collected for measurement of serum creatinine and routine tests. Women of childbearing potential must undergo a pregnancy urine test.

A C-SSRS assessment, will be performed at each of these visits, as well as a vital signs assessment. In addition, a hemolysis panel on diverted blood sample (see [Section 11.5](#)) will be done at the Month 4 and Month 8 visits.

All patients should undergo assessment of prior and concomitant medication and AEs.

CCI  
[Redacted text block]

CCI  
[Redacted]

Study treatment administration by IV infusion, will be performed within 30 min after the EDS process has been completed.

The satellite sample bag will be detached and used for sterility culture tests: a sample of the EDS-EP (approximately 1 ml per inoculum for a total of 2 mL) will be collected to perform a sterility test using a culture-based method as presented in [Appendix 10](#). A 1-mL sterile sample of the EDS-EP will be stored under refrigeration as a "Retention Sample". In case of positive/contaminated post-release sterility results, an action plan has been established as presented in [Section 13.6](#) and in [Appendix 11](#).

After completion of the IV infusion of the study treatment the following assessments will be performed: Vital signs, physical examination (1-2 hr after infusion), assessment of AEs, and assessment of concomitant medications

*Months 6 and 12*

At Months 6 and 12 the following assessments will be performed before treatment administration: all assessments of efficacy (ICARS, CGI-C, CGI-S and EQ-5D-5L) and safety (vital signs, ECG, routine laboratory tests on the diverted blood samples (see [Section 11.5](#)), physical and neurological examinations, C-SSRS, BMD and assessments of AEs and concomitant medication use), as well as special laboratory tests (HbA1c, CD4+ lymphocytes count and CRP), on the diverted blood samples (see [Section 11.5](#)). A serum (on the diverted blood samples, see [Section 11.5](#)) and urine pregnancy test will be performed for women of childbearing potential. Physical development, sexual maturation, and the effect of treatment with dexamethasone on these aspects will be assessed (Tanner scale). Tanner staging of the breasts in pre-menarchal females and of the scrotum in males who have not completed puberty, will be performed at Months 6 and 12. Post-menarchal females and males who have completed puberty will be excluded from this growth analysis.

CCI  
[Redacted]

Study treatment administration by IV infusion, will be performed within 30 min after the EDS process has been completed.

CCI  
[Redacted]

After completion of the IV infusion of the study treatment, a physical examination and vital signs will be performed (1-2 hr after infusion), as well as assessments of AEs and concomitant medication use.

A Month 12 infusion, and all of the associated procedures, would only be done in patients who are continuing open label treatment past one year. The schedule of visits and assessments for the first 12 months - as described above- will be replicated for the second year onwards.

*Safety Follow-up Visit*

All patients who discontinue will be required to return for a Safety Follow-up Visit approximately 60 days ( $\pm$  7 days) after their last infusion. At this visit, plasma cortisol, hemolysis panel, pregnancy status (for women of childbearing potential), C-SSRS, and vital signs will be assessed, as well as the occurrence of any AEs or Serious AEs (SAEs) reported by the patient/caregiver or observed by the Investigator since the previous visit.

*Evaluation and Infusion Schedule*

The monthly infusions should be performed every 21-28 days. A window of + 10 days will be permitted on each of the scheduled monthly visits. Therefore, no EDS-EP infusion should be performed less than 21 days or more than 38 days after the previous infusion. The window between an infusion and the subsequent one should be kept as regular as possible throughout the study, avoiding fluctuations in administration windows. The date of an infusion is not bound to the date of the initial treatment but to the date of the previous IMP administration. Infusions should not be skipped; therefore, if necessary, the infusion schedule can be modified to conform to the above guidelines.

